5.1 General study design

Patients will be enrolled to reach 30 evaluable subjects on this phase I patient-blinded, randomized controlled trial investigating the feasibility and safety of intratumoral 1% lidocaine injection at the time of direct laryngoscopy prior to definitive surgery in HPV associated OPSCC patients. Patients with a clinically apparent primary tumor (i.e. clinical T1-T4), any clinical N stage, and M0 disease (per AJCC 8th Edition) undergoing direct laryngoscopy who are being considered for definitive TORS and selective neck dissection, will be eligible. Patients will be blinded to the intervention which will be administered as dictated by the protocol, according to Section 3.1 above. Randomization will be performed using the “Clinical Trial Randomization Tool” from The National Cancer Institute's Division of Cancer Prevention.⁸¹

Clinical evaluations will be performed according to routine clinical care, which is left to the discretion of the treating physician. This will include a baseline evaluation prior to direct laryngoscopy/study intervention.

All patients will be asked to take a short survey about pain (2 questions) at their follow up appointment after their direct laryngoscopy and biopsy.

Locoregional recurrence will be defined as biopsy-proven recurrent squamous cell carcinoma at the original, primary tumor site, or in the neck.

5.2 *Surgery*

Surgery will be performed per standard of care consisting of TORS primary site resection, selective neck dissection, and external carotid artery vessel ligation. The decision to stage the neck dissection and TORS will be determined at the discretion of the head and neck surgeon. Intraoperative continuous monitoring of circulation and respiration will be performed.

5.3 *Radiation Therapy*

Patients who have indications post-operative radiation therapy per NCCN guidelines⁵ will be referred to a radiation oncologist who specializes in the treatment of head and neck cancer within the University of Pennsylvania Health System, with the decision on whether to treat with radiation therapy determined at the discretion of the consulting radiation oncologist.

If the patient meets eligibility criteria for the published AVOID trial which is institutional standard of care for HPV associated OPSCC,¹⁹ then the primary site will be spared, without compromising coverage to the neck volumes. The eligibility for this approach is patients with pT1-T2, negative margins (defined as ≥ 2 mm), no perineural invasion (PNI), and no lymph-vascular space invasion (LVSI).

Simulation for treatment is required. CT-based treatment planning is required. Treatment with either IMRT or PBT is allowed. All fields will be treated every session. Interruptions in therapy should be discussed with the principal investigator but will be instituted at the discretion of the treating radiation oncologist. Dose calculation should be performed using inhomogeneity corrections to account for differences in tissue density across the head and neck region. Patients may miss up to three treatments a week due to illness, travel, etc.

5.4 *Chemotherapy*

Patients who have indications for the use of concurrent chemotherapy in the postoperative setting (ENE or positive margins)⁸² will be referred to a medical oncologist who specializes in the treatment of head and neck cancer within the University of Pennsylvania Health System, with the decision on whether to treat with chemotherapy determined at the discretion of the consulting medical oncologist.

5.5 *Blood Draws*

Research blood draws will be obtained at the following time points:

- 1) Prior to direct laryngoscopy/study intervention on the day of surgery. This will typically be performed in the preoperative area or operating room when obtaining an IV for surgery.
- 2) After direct laryngoscopy/study intervention (but before definitive surgery or radiation). This will typically be performed on the day of the post-laryngoscopy clinic visit to discuss the results of the direct laryngoscopy.

Other blood draws will be obtained according to institutional standard of care.

5.6 *Sample Storage*

Tumor tissue from biopsy and surgery or other collected samples (e.g., blood, serum) may be used or stored for any other future relevant analysis. Specific technical studies in the future could include pathology, immunohistochemical, genetic, genomic, proteomic, or transcriptomic analyses. The tissue may include paraffin blocks or fresh tissue that is frozen.

5.7 *Study Visit Schedule*

An outline of the typical study visit schedule is provided below. There will be no planned additional study visits compared to routine, standard of care (SOC). Clinical research procedures are underlined in the table for clarification purposes.

Visit Number	Visit Procedures
Visit 1	Come to the clinic for a routine (SOC) clinic visit(s). Decide if you want to participate in the study, ask questions, sign the consent form if you do want to participate.
Visit 2	Have a pre-operative research blood draw with blood sample storage on the day of your direct laryngoscopy with biopsy.

	
Study Intervention: Participants will be randomly assigned to two groups.
 
 • Group 1 (Intervention Arm) – Biopsy and injection of lidocaine into tumor while you are under general anesthesia for your direct laryngoscopy. • Group 2 (Control Arm) – Biopsy without injection of lidocaine while you are under general anesthesia for your direct laryngoscopy.
Visit 3	Routine (SOC) clinic visit to discuss the results of your direct laryngoscopy with biopsy and have a research study blood draw with blood sample storage . You will also be asked to take a short survey.
Visit 4	Routine (SOC) treatment with primary surgery or primary radiation with storage of tumor tissue for research . This will allow researchers to study leftover tissue removed during your routine care.
Visit 5	Routine (SOC) follow up for cancer surveillance per National Comprehensive Cancer Network guidelines.

6 Statistical Plan

This study is considered exploratory because, to our knowledge, no prior published data exists on the effects of lidocaine injection on pathologic tumor response, survival, and recurrence in HPV associated OPSCC. The planned sample size for this phase I trial is 30 evaluable subjects split equally between the intervention and control arms. Subjects will need to have a definitive diagnosis of HPV associated OPSCC and undergo surgery (TORS and neck dissection) to be considered evaluable.

The co-primary objectives of this study are to determine safety and if the proportion of patients with pTR-2 in the primary tumor is different in the intervention group compared to the control arm. All enrolled participants, regardless of HPV status or final pathology, will be included in the primary safety analysis. Thus, any adverse events or dose-limiting toxicities observed in participants will contribute to the overall safety assessment of intratumoral lidocaine.

For the pathologic response primary endpoint, H_0 is that there is no difference in the proportions of patients with pTR-2 between the intervention or no intervention (control) groups; H_a is that the intervention arm is associated with a higher proportion of pTR-2. The proportion of pTR-2 will be compared between the intervention and control arms using a one-sided Fisher's exact test with a significance level of 0.05. A 95% confidence interval will be used. We estimate that a sample size of 30 patients is needed to allow us to detect

with 80% power at the one-sided alpha level of 0.05 a major pathologic treatment rate of 30% in the intervention arm compared to 0% in the control arm.

In addition to hypothesis testing for the pathologic response primary outcome, we will use within-between interaction models to account for the effects of the treatment and the interaction between treatment and patient and disease factors including age, sex, disease stage, and adverse pathologic features (e.g. tumor grade, perineural invasion, lymphovascular invasion). We will estimate means and standard deviations for each group and the correlation within subjects to better understand the relationship between repeated measures. We will use mixed-effects models to handle within-subject correlations and between-subject comparisons.

The secondary endpoints include 2-year locoregional control (LCR) rates, progression-free survival (PFS), metastasis-free survival (MFS), and overall survival (OS). PFS will be defined as time from random assignment to disease progression or death from any cause. MFS will be defined as time from random assignment to first evidence of distant metastatic disease or death from any cause. OS will be defined as the time from random assignment and death due to any cause. 95% confidence intervals will be used. LRC rates, PFS, MFS, and OS will be estimated using the Kaplan–Meier method, and log-rank test will be used to compare the two groups using a significance level of 0.05.

Due to distinct biological differences between HPV associated and HPV-negative OPSCC and evidence suggesting that lidocaine's anticancer effects may be more relevant to HPV associated tumors, any HPV-negative tumors will be evaluated separately from HPV associated tumors for primary and secondary efficacy endpoints.

An interim analysis is not planned due to the well-established safety data associated with injectable lidocaine.

7 Safety and Adverse Events

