Number of Subjects	30 evaluable subjects
Diagnosis and Main Inclusion Criteria	
 - ≥18 years old with OPSCC undergoing direct laryngoscopy for consideration of TORS and neck dissection.
Study Regimen	
 - Patients will be randomized and blinded to intratumoral injection of 1% lidocaine (intervention arm) or no injection (control arm) at the time of direct laryngoscopy and biopsy prior to TORS and neck dissection. 
 o Intervention arm: While under general anesthesia after direct laryngoscopy with biopsy, 1% lidocaine will be injected under direct visualization (not exceeding the maximum tolerated dose of 4.5 mg/kg body weight) into the primary tumor with the aim to distribute the lidocaine evenly into the tumor. o Control arm: Direct laryngoscopy with biopsy with no injection. - Blood samples will be obtained before and after direct laryngoscopy/study intervention. - Pathologic tumor response (pTR) will be determined from surgical specimens.

Statistical Methodology	
This is a patient-blinded, randomized phase I study assessing safety, pathologic treatment effects, and oncologic outcomes from intratumoral lidocaine injection vs no injection at the time of direct laryngoscopy prior to TORS and neck dissection for HPV associated OPSCC. The total sample size is estimated to be 30 patients total (split approximately equally between the two groups). The proportion of patients with a pathologic tumor response (pTR) $\geq 50\%$ (pTR-2) in the primary tumor following surgical resection will be compared between intervention and control arms using a one-sided Fisher's exact test with a significance level of 0.05. The 2-year locoregional control (LRC) rates, progression-free survival (PFS), metastasis-free survival (MFS), and overall survival (OS) will be estimated using the Kaplan–Meier method and compared using log-rank test between the two arms.

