3.1 General Design

This is a phase I patient-blinded, randomized controlled trial evaluating intratumoral lidocaine injection prior to definitive surgery in HPV associated OPSCC. Patients with OPSCC undergoing direct laryngoscopy who are being considered for definitive TORS

and selective neck dissection, will be eligible. Patients will be randomized and blinded to intratumoral injection of 1% lidocaine (intervention arm) or no injection (control arm) at the time of direct laryngoscopy. After administration of general anesthesia and biopsy, lidocaine will be injected under direct visualization (not exceeding the maximum tolerated dose of 4.5 mg/kg body weight) into the primary tumor. The control arm will receive no injection.

Blood samples will be obtained prior to direct laryngoscopy/study intervention (pre-biopsy) and again after the intervention (post-biopsy). The pTR rate (defined above and in published literature^{78, 79}) will be determined by the designated study pathologist ([name], PhD) with head and neck expertise using increments of 10% for the biopsy and surgery specimens. The scores will be grouped as pTR-0 (<10%), pTR-1 (10%–49%), and pTR-2 (≥50%).

Patients will otherwise receive institutional standard of care treatment including TORS primary site resection, selective neck dissection, and additional indicated adjuvant radiation therapy with or without chemotherapy. All enrolled patients will be assessed for safety measured by adverse events. If a patient does not ultimately receive primary surgery following their direct laryngoscopy/study intervention (based on surgical candidacy, patient preference, or other reasons), then they will not be counted as an evaluable subject, as the primary endpoint pTR requires a surgical specimen for evaluation. If a patient is determined to have a pathology other than HPV associated OPSCC after their direct laryngoscopy, then they will not be counted as an evaluable subject.

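### The one-sided Fisher exact test for pTR-2 is valid but conservative; a Boschloo exact test at the same 0.05 would gain power for some unequal splits or a non-zero control rate, though none at 15 v 15 with 30% v 0%

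*Protocol*

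**What the plan says.** Protocol Section 6 and the Statistical Methodology row of the Study Summary both name a one-sided Fisher "exact test with a significance level of 0.05" for the proportion with pTR-2. Section 6 gives the sample-size statement: "We estimate that a sample size of 30 patients is needed", "with 80% power at the one-sided alpha level of 0.05", for a "rate of 30% in the intervention arm compared to 0% in the control arm".

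On allocation, Section 6 plans "30 evaluable subjects split equally between the intervention and control arms", while the Summary says only "split approximately equally between the two groups". Section 5.1 states that "Patients will be enrolled to reach 30 evaluable subjects", which is a total and not a number per arm. Under Section 3.1, a patient who does not go on to primary surgery is left out after randomization: "then they will not be counted as an evaluable subject, as the primary endpoint pTR requires a surgical specimen for evaluation". The same section also leaves out patients whose pathology proves to be other than HPV-associated disease.

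Section 6 calls the study exploratory. It says nothing about the attained size of the Fisher test and does not mention an unconditional exact test.

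**The concern.** Fisher's test conditions on the total number of responders. In a small trial with few responders that leaves very few possible outcomes, so the attained type I error can fall far below the nominal level. The pTR-2 comparison is the only test in the protocol with a power statement, and 30 patients leave little to spare. If another exact test keeps the same declared 0.05 and never rejects less often, part of the power lost to conservatism can be avoided at no cost in patients.

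The question is where that gain occurs. It depends on the final split of evaluable patients and on the control response rate, and the protocol guarantees neither.

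**Working it through.** **Inputs.** From the protocol: one-sided alpha 0.05, 30 evaluable patients, planned 15 v 15, true rates 30% v 0% (Section 6). Unequal splits and non-zero control rates are assumptions, used to show the range. Splits are written intervention/control.

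**The plan's own figure.** The protocol does not say how 80% was obtained. An unpooled normal approximation gives n per arm = (1.645 + 0.842)² × (0.3 × 0.7 + 0 × 1) / 0.3² = 14.4, so 15 per arm and 30 in total, with approximate power 81.3%. That reproduces N = 30, but it is not the power of the planned test.

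**Fisher at 15/15, 30% v 0%.** With no control responders the one-sided p-value for x responders is C(15,x)/C(30,x).
- 3 v 0: 455/4,060 = 0.112, not rejected.
- 4 v 0: 1,365/27,405 = 0.0498, rejected.

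Power is P(X ≥ 4) for a binomial with n = 15 and rate 0.3: 1 − (0.0047 + 0.0305 + 0.0916 + 0.1700) = 70.3%.

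**Boschloo at 15/15.** The test orders tables by Fisher's p-value, then takes the largest rejection probability over all common response rates. It gives 0.0593 for 3 v 0 (not rejected) and 0.0216 for 4 v 0 (rejected). The boundary with an empty control arm is therefore the same, and so is the power of 70.3%. The tests part once the control arm has a responder: 5 v 1 has Fisher p = 0.0843 but Boschloo p = 0.0495.

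**Attained size.** Enumerating all tables at 15/15, the maximum over the common rate is 2.16% for Fisher and 4.95% for Boschloo. For splits from 11/19 to 19/11, Fisher lies between about 2.2% and 2.9% and Boschloo stays below 5%.

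**Power at 30% v 0%, by split of the 30 evaluable patients:**

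| Split | Responders needed v 0: Fisher / Boschloo | Power: Fisher | Power: Boschloo |
|---|---|---|---|
| 10/20 | 3 / 3 | 61.7% | 61.7% |
| 11/19 | 3 / 3 | 68.7% | 68.7% |
| 12/18 | 4 / 3 | 50.7% | 74.7% |
| 13/17 | 4 / 3 | 57.9% | 79.8% |
| 14/16 | 4 / 4 | 64.5% | 64.5% |
| 15/15 | 4 / 4 | 70.3% | 70.3% |
| 16/14 | 5 / 4 | 55.0% | 75.4% |
| 17/13 | 5 / 4 | 61.1% | 79.8% |

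At 16/14, for example, 4 v 0 has Fisher p = C(16,4)/C(30,4) = 1,820/27,405 = 0.0664 and Boschloo p = 0.0331. Moving one patient from 15/15 to 16/14 lowers Fisher's power by 15.3 points (70.3 − 55.0) and raises Boschloo's by 5.1 (75.4 − 70.3).

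**Power at 15/15 with an assumed non-zero control rate:**

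| True rates | Fisher | Boschloo |
|---|---|---|
| 30% v 2% | 58.4% | 63.3% |
| 30% v 5% | 43.5% | 52.2% |
| 40% v 10% | 46.3% | 59.2% |

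**The case against.** The strongest reply is that nothing here is wrong. Fisher's test is standard, pre-specified and stated the same way in both places; it holds its level, and the study calls itself exploratory. At the design the protocol actually plans, Boschloo adds nothing. All of this stands, and it is why the point is a suggestion only.

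Three stronger readings are tempting, and the documents do not support them.
- A reader might infer that the low size explains why the planned comparison falls short of 80%. It does not: at 15/15 with 30% v 0% both tests have the same boundary and the same 70.3%.
- A reader might infer that 15/15 is the only split without a gain. At a 0% control rate, 14/16, 11/19 and 10/20 gain nothing either. With a non-zero control rate the gain can also be negligible: 11/19 at 30% v 5% moves only from 46.4% to 47.1%.
- A reader might average over coin-flip allocation and quote one overall gain. Section 5.1 names a randomization tool but no allocation method, so such an average rests on an assumption the protocol does not make.

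Nor is Fisher's conservatism without benefit: it more than halves the worst-case false-positive rate. That is a genuine trade, although at low response rates the difference is small (at a common rate of 10%, 1.2% against 1.6%).

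What the reply does not remove is the uncertainty about the split. Patients leave the evaluable set after randomization, enrolment runs to a total, and the Summary promises only approximate equality. The protocol does not show how exactly 15 evaluable patients per arm would be secured.

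**Conclusion.** The point holds as a low-priority improvement. The planned test is valid but conservative, with a maximum true size of 2.16% at 15/15 against a declared 5%. Boschloo's test keeps the declared level and is never less powerful.

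The gain depends on the configuration. It is zero at the planned 15/15 with 30% v 0%. It is about 19 to 24 points at 12/18, 13/17, 16/14 and 17/13 with 30% v 0%, and about 5 to 13 points at 15/15 for the assumed control rates of 2% to 10% shown. How likely these configurations are cannot be derived from the protocol: the size of any imbalance is unknown, and the control rate of 0% is itself a planning assumption.

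The stated 80% is a separate matter. For the planned Fisher test at 15/15 and 30% v 0% the power is 70.3%, and the change of test leaves that figure as it is.

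**What to change.** In Section 6 and in the Statistical Methodology row of the Study Summary, name a one-sided Boschloo exact unconditional test at significance level 0.05 as the primary test for pTR-2, and state that Fisher's one-sided p-value will be reported alongside. Make the change before any pTR result is seen; a later switch would look data-driven.

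The cost is one sentence in each of two places. Standard software runs the test, and neither the sample size nor the declared alpha changes. There are two downsides: the test is less familiar to readers, and the attained maximum false-positive rate rises from about 2% towards, but not above, the declared 5%.

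Separately, restate the power in Section 6 as that of the test finally chosen: 70.3% at 15/15 for 30% v 0% under either test.

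### The 80% power claimed for pTR-2 is wrong for the planned test: one-sided Fisher's exact test with 15 v 15 has 70.3% power for 30% v 0%, and no other split of 30 does better

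*Protocol*

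**What the plan says.** Section 6 (Statistical Plan) of the protocol gives every input to the calculation in two neighbouring paragraphs.

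- **Size and allocation:** "30 evaluable subjects split equally between the intervention and control arms". The Study Summary is slightly looser: "split approximately equally between the two groups".
- **Test:** pTR-2 is compared one-sidedly by Fisher's method, an "exact test with a significance level of 0.05". The Study Summary names the same test and level.
- **Power claim:** 30 is presented as the number needed, and the power and planning effect are given as "with 80% power at the one-sided alpha level of 0.05 a major pathologic treatment rate of 30% in the intervention arm compared to 0" per cent for controls.

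The 30 are evaluable subjects. Section 5.1 says enrolment continues until that number is reached, so dropout plays no part in the power figure. The power sentence names no method other than the test given just before it.

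**The concern.** With 15 patients per arm and a control rate of 0%, Fisher's exact test is coarse. It can reject only when the lidocaine arm reaches a whole number of responders, and one patient more or fewer moves the p-value a long way. Normal-approximation formulas ignore this and are unreliable when one rate is zero. A round 80% at N = 30 therefore needed checking against the test that will be used.

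The power sentence is the protocol's only quantitative justification for 30 patients, and pTR-2 is a co-primary endpoint with its own hypotheses and alpha. If the true power is lower, reviewers are approving the trial on a wrong figure. A non-significant result would also be read as having a 20% chance under the planning effect when the real chance is larger.

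**Working it through.** **Inputs** (all from Section 6): one-sided Fisher's exact test, alpha 0.05, n = 15 per arm, true pTR-2 rate 0.30 on lidocaine and 0 on control.

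**Can 80% be reproduced?** With the named test, no. Several approximations were tried at 15 per arm, one-sided 0.05:

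| Method | Power |
|---|---|
| Unpooled normal (Wald) | 81.3% |
| Pooled normal | 76.5% |
| Arcsine | 93.7% |
| Fisher's exact (the planned test) | 70.3% |

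The unpooled formula has standard error √(0.30 × 0.70 / 15) = 0.1183. Then 0.30 / 0.1183 − 1.645 = 0.891, and Φ(0.891) = 0.813. At 14 per arm it gives 79.0%, so 15 is the smallest arm size at which that formula reaches 80%. This is a plausible origin of the figure, but it is an inference: the protocol does not state its formula.

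**Step 1: rejection boundary of the planned test.** A true control rate of 0% means the control arm always has 0 responders of 15. With k lidocaine responders, the one-sided p-value is C(15,k) / C(30,k).

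- k = 3: 455 / 4,060 = 0.112, not significant
- k = 4: 1,365 / 27,405 = 0.0498, significant

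At least 4 responders of 15 are needed.

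**Step 2: power.** With X ~ Binomial(15, 0.30):

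P(X ≤ 3) = 0.0047 + 0.0305 + 0.0916 + 0.1700 = 0.2969 (terms rounded)

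Power = 1 − 0.2969 = **0.703**. The shortfall against the stated figure is 80 − 70.3 = 9.7 percentage points.

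**Step 3: other splits of 30.** The same calculation was run for all 29 splits, from 1/29 to 29/1. The maximum is 70.3% at 15/15 and the next best is 68.7% at 11/19. Splits near equality (lidocaine/control):

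| Split | Responders needed | p at that number | Power |
|---|---|---|---|
| 13/17 | 4 | 715 / 27,405 = 0.0261 | 57.9% |
| 14/16 | 4 | 1,001 / 27,405 = 0.0365 | 64.5% |
| 15/15 | 4 | 0.0498 | 70.3% |
| 16/14 | 5 (4 gives 1,820 / 27,405 = 0.0664) | 4,368 / 142,506 = 0.0307 | 55.0% |
| 17/13 | 5 | 6,188 / 142,506 = 0.0434 | 61.1% |

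One patient moving from control to lidocaine costs 70.3 − 55.0 = 15.3 points, because p at 15/15 only just clears 0.05.

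**Step 4: what would give 80%.** At 15/15, solving P(X ≥ 4) = 0.80 gives a true lidocaine rate of 33.7%. Holding 30% v 0% and strictly equal arms, power is 76.2% at 20 per arm and first reaches 80% at 21 per arm (80.2%).

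**Step 5: dependence on the 0% control rate.** With 15/15 and 30% on lidocaine, power is 64.1% if the true control rate is 1%, and 43.5% if it is 5%.

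**The case against.** The study is phase I. Section 6 calls it exploratory because no earlier data exist on this effect. Safety is the other co-primary endpoint and is analysed in all enrolled participants whatever the pTR-2 power. The sample size is offered as an estimate, and the 30% and 0% have no cited source, so a precise power figure can be seen as having limited meaning. The power sentence does not itself name a method, and a common normal approximation gives 81.3%. The figure may thus be a planning approximation rather than a slip. Finally, 21 per arm overstates what the exact test requires, since its power moves in a saw-tooth: 18 lidocaine and 19 control (37 in total) already give 83.5%.

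Some of this stands. Exploratory status softens the consequence and can justify accepting lower power. The approximation probably explains the 80%. The 21 per arm is only the first strictly equal-arm size to reach 80%; it should not be read as a minimum total of 42.

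None of it makes the sentence true. The protocol sets a null hypothesis, an alternative, an alpha, a test and a power for this endpoint, and the power is not that of the test. The looser wording on allocation in the Study Summary does not help either, because every unequal split of 30 has lower power. A separate analysis plan could not rescue a figure that the protocol itself states.

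**Conclusion.** The stated power is wrong as written. For the planned one-sided Fisher's exact test at 0.05, 30 evaluable patients give at most 70.3% power for 30% v 0%, against 80% claimed. The probability of missing the planning effect is 29.7% rather than 20%.

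This rests only on inputs that the protocol fixes, and it is the favourable case, since it assumes exactly 15 evaluable patients in each arm and a control rate of exactly 0%. Unequal arms are a real possibility: under Section 3.1, patients who do not go on to primary surgery, or whose pathology proves not to be HPV-associated, stop being evaluable after the study intervention.

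**What to change.** Keep 30 evaluable subjects and replace the power sentence in Section 6 with wording such as:

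> With 15 evaluable subjects per arm, the one-sided Fisher's exact test at 0.05 has about 70% power to detect 30% v 0% (80% power for about 34% v 0%). Power is lower if the evaluable arms are unequal (64.5% at 14 lidocaine/16 control, 55.0% at 16/14) or if the control rate is above 0% (64.1% at 1%).

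The claim that 30 patients are needed for 80% power then goes. The sponsor should give the actual basis for 30 in its place. If that basis is feasibility, Section 4.7 already has the accrual estimate to cite.

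The cost is a sentence or two of protocol wording. No extra patients are needed, and the test, alpha and conduct stay the same. The stated power becomes less favourable.
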